## BACKGROUND

Studies across more than three decades have revealed diverse health benefits from human-animal interaction, including effects on social behavior, mood, stress and anxiety, and physical health. However, relatively little is known about the underlying biological mechanisms which mediate these outcomes, precluding a deeper understanding of how and why human-animal interaction works. Recent studies indicate that human-animal interaction can lead to acute release of oxytocin in human adults, a neuropeptide that plays critical roles in the development and expression of social behavior, cognition, stress physiology, and physical health. Dysregulation of the oxytocin system has been implicated in a range of diseases and/or disabilities, including autism, post-traumatic stress disorder, and anxiety disorders. Exogenous oxytocin administration has shown some promise as an experimental therapeutic, but knowledge about its long-term safety or efficacy is limited, and current administration routes rely on flooding the periphery with supraphysiological concentrations of synthetic oxytocin (only minute amounts of which cross the blood-brain barrier). In contrast, human-animal interaction may provide a safe and effective method for stimulating endogenous oxytocin activity in the central nervous system. However, no studies have investigated how human-animal interaction affects oxytocin release in children. This study was designed to assess the effects of human-animal interaction on oxytocin release in children. Because oxytocin can be released in response to both pleasurable stimuli and stress, salivary cortisol was also measured as a biomarker of acute stress, to contextualize findings regarding oxytocin.

## PROTOCOL

### Participants

*Eligibility criteria:* Children were eligible for inclusion if they were between 8-10 years of age, lived with a companion dog who had been in the household for at least 6 months, and did not meet any of the exclusionary criteria. Exclusionary criteria for children included current use of psychoactive medications or diagnosis with neurodevelopmental or endocrine diseases / disorders.

*Recruitment:* Participants were recruited from the local community through email listservs, print advertisements, social media, and flyers distributed to schools, libraries, museums, and veterinary clinics. Parents received monetary compensation and children were allowed to select a small toy to bring home after each study visit.

### Procedure

## Materials

The study was conducted at the Arizona Canine Cognition Center (ACCC) in Tucson, Arizona in an indoor room with padded floor mats. A chair was set up in the corner of the room. Video was recorded from two overhead cameras and two tripod-mounted cameras and audio was captured using two room microphones. Brown noise was played through two wall-mounted speakers to mask distracting noises from outside the experiment room.

## General Procedure

Participants visited the ACCC three times and completed one of three conditions at each visit: Pet Dog (PD), Unfamiliar Dog (UD), and Control (CT). Conditions were scheduled in two fixed orders (UD-CT-PD or PD-CT-UD), and the order was counterbalanced across participants.

Upon arrival, participants were greeted by two experimenters. Baseline (T1) saliva samples were then collected from the child (see *Sample Collection*). The parent was provided with an iPad and headphones and instructed to sit in a chair facing a corner of the room and to ignore the child and dog (when applicable) until the end of the final sample collection. The experimenters then left the child in the room to engage in the target activity and returned 15 minutes later to collect timepoint 2 (T2) saliva samples from the child. Experimenters then left the room and children were allowed an additional 10 minutes to engage in the activity. Timepoint 3 (T3) saliva samples were collected fifty minutes after the start of the behavioral activity.

*Pet Dog (PD) condition:* In the PD condition, children were given the opportunity to interact naturally with their pet dog. Children were informed that they would be left in the room with their dog, and to “keep the dog company” during this time. They were further instructed that they could play with their dog however they liked and were briefly reminded about appropriate and inappropriate interactions with dogs (e.g. not okay to pull a dog’s tail or step on a dog; okay to pet a dog gently or to play with a ball together).

*Unfamiliar Dog (UD) condition:* The UD condition was identical to the PD condition with the exception that children interacted with a dog that they had not met prior to the study. This dog was a Labrador retriever who was released from a service dog program for a benign medical condition. Children were shown a photo of the dog prior to meeting her and informed that she had a mellow personality and enjoyed belly rubs.

*Control condition (CT):* In the CT condition, a table and chair were set up in the middle of the experiment room, and children were provided with a box of toys that included LEGOs, kinetic sand, a Lite-Brite, various puzzles, and colored pencils and drawing paper. Children were instructed that they could play with whichever toys they liked.

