## STATISTICAL ANALYSIS PLAN

The **primary outcome measure** was the oxytocin output (relative to baseline) in conditions involving human-animal interaction (pet dog, unfamiliar dog) relative to the nonsocial control condition. The area under the curve with respect to the initial value (AUCi) was used as the measure of oxytocin output. We compared AUCi values across conditions using a Bayesian linear mixed model. In addition to the focal predictor variable (experimental condition), the model included covariates for participant sex, age (years), assay plate, and study visit number. Participant ID was included as a random intercept in the model.

The **secondary outcome measure** was the cortisol output (relative to baseline) in the conditions involving human-animal interaction (pet dog, unfamiliar dog) relative to the nonsocial control conditions. Analysis of this endpoint was conducted identically to that for oxytocin, as described above, with the exception that the model did not include a covariate for assay plate.

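### Control is always the second visit, so both dog-versus-control comparisons absorb any departure of visit 2 from the midpoint of visits 1 and 3, and the plan does not bound it

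*Combined protocol and SAP*

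**What the plan says.** The General Procedure describes a three-period crossover: "Participants visited the ACCC three times and completed one of three conditions at each visit". The schedule is: "Conditions were scheduled in two fixed orders (UD-CT-PD or PD-CT-UD), and the order was counterbalanced across participants". No counts per order are given.

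The Statistical Analysis Plan defines the primary outcome as "oxytocin output (relative to baseline) in conditions involving human-animal interaction (pet dog, unfamiliar dog) relative to the nonsocial control condition". On scale it says: "The area under the curve with respect to the initial value (AUCi) was used as the measure of oxytocin output". On adjustment it says "the model included covariates for participant sex, age (years), assay plate, and study visit number", and then: "Participant ID was included as a random intercept in the model". It does not say whether visit number is linear or categorical, and it gives no priors for the Bayesian model. For cortisol, "Analysis of this endpoint was conducted identically to that for oxytocin", apart from dropping assay plate, so visit number stays in that model too.

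The plan contains no sensitivity analysis for visit effects and no statement of what dog versus control assumes about visit 2.

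**The concern.** Every control measurement comes from visit 2 and every dog measurement from visit 1 or 3. Counterbalancing exchanges the two dog conditions between the outer visits, so it protects the contrast between them. It does not protect either dog condition against control, and that is the comparison on which both outcomes are judged. A reader who sees visit number in the model would suppose that visit effects have been dealt with.

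Two mechanisms are conceivable; neither is shown to occur.

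- **Arrival response.** A child may arrive aroused at the first visit and then settle. The Background itself notes that stress as well as pleasure can release oxytocin.
- **Carry-over.** Every control visit directly follows a dog visit and no dog visit does. Any after-effect, such as expecting a dog, would fall on control alone.

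Either could be reported as a dog effect or could hide a real one.

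**Working it through.** The plan states no sample size, SD or error rate, so it has no figure to reproduce. The structural results in steps 1 to 4 need only the two orders and the model; step 3 also assumes T1 at minute 0.

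**1. Rank of the fixed effects (condition plus visit).**

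| Visit coding | Columns | Rank | Dog − control |
|---|---|---|---|
| Linear | 4 | 4 | estimable |
| Linear + quadratic | 5 | 4 | not estimable |
| Categorical | 5 | 4 | not estimable |

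In the categorical case the PD, UD and visit-2 indicators sum to 1 in every row. Pet dog minus unfamiliar dog is estimable under all three codings.

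**2. Bias with linear visit.** Pooled dog minus control is the average over children of (visit 1 + visit 3)/2 − visit 2. With no condition effect its expectation is (v1+v3)/2 − v2. PD − CT and UD − CT carry the same bias; PD − UD carries none. With no visit term the pooled bias is the same, and so are the separate ones if the orders are 1:1. The fitted slope per visit is (v3−v1)/2.

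| Visit effects (v1, v2, v3) | Dog − CT bias | Fitted slope |
|---|---|---|
| (−1, 0, 1) straight line | 0 | +1 |
| (1, 0, 0) first visit only | +0.50 | −0.50 |
| (0, 1, 0) visit 2 only | −1 | 0 |
| carry-over c from a dog visit | −c | 0 |

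**3. What AUCi removes.** With samples at 0, 15 and 50 minutes, the trapezoid rule weights T1, T2 and T3 by −42.5, +25 and +17.5. These sum to zero, so a shift common to all three samples cancels. A rise of 1 unit in T1 alone does not. At visit 1 it moves dog − CT by −42.5/2 = −21.25 and the slope by +21.25. At visit 2 it moves dog − CT by +42.5 and the slope by 0.

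**4. A bound for monotone visit effects.** If v2 lies between v1 and v3, then |(v1+v3)/2 − v2| ≤ |v3−v1|/2, the absolute slope, which the data estimate. A peak or trough at visit 2 escapes this bound.

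**5. Categorical visit under assumed priors.** With a true departure of 0.5 SD and no dog effect, the posterior mean of dog − CT ran from 0.00 to 0.49 depending on the prior SDs. With prior SD 1 on both condition and visit it was 0.161 at n = 40 and 0.166 at n = 400.

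**6. Scale (illustration only).** Assumed: residual SD 1, orders 1:1, linear visit, a 1.96 rule and no dog effect. The pooled contrast has variance (¼ + ¼ + 1)/n = 1.5/n and the slope (¼ + ¼)/n = 0.5/n, with covariance 0. At n = 20, 40 and 80 the standard errors are 0.274, 0.194 and 0.137 for the contrast, and 0.158, 0.112 and 0.079 for the slope.

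| Departure | Dog − CT excludes 0, n = 20 / 40 / 80 | Slope interval excludes 0 |
|---|---|---|
| Visit 1 only, 0.25 SD | 7 / 10 / 15% | 12 / 20 / 35% |
| Visit 1 only, 0.5 SD | 15 / 25 / 45% | 35 / 61 / 89% |
| Visit 1 only, 1.0 SD | 45 / 73 / 95% | 89 / 99 / 100% |
| Visit 2 only, 0.5 SD | 45 / 73 / 95% | 5% throughout |

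**7. Tipping point.** For a pooled estimate of 0.50 SD the conclusion changes at d = 0.50 − 1.96 × SE: 0.12 at n = 40 and 0.23 at n = 80. With a fitted slope of 0, the slope's interval limits are ±0.22 and ±0.15. The conclusion fails over that range at n = 40 and survives at n = 80.

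**The case against.** The strongest reply is that this is a possible bias, not a demonstrated one. With only two orders, putting control in the middle makes dog versus control immune to a straight-line trend, AUCi removes shifts common to a whole visit, and what remains is curvature in the within-visit response. All of that is true. It narrows the problem but does not remove it, because the visit covariate cannot supply the missing protection under any coding.

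The second reply is that the bound misses the worst case. Carry-over onto control leaves the slope at zero. If one required the conclusion to hold over the slope-based range, a visit-2-only departure of 0.5 SD would still give a false conclusion in 29%, 56% and 88% of studies at n = 20, 40 and 80 (range set by the estimated slope), or 5%, 18% and 54% (range set by its interval limits). A true effect of 0.50 SD would pass equally often. This stands: the range is informative only if the visit effect is monotone, and this schedule cannot test that.

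Third, the illustration uses the pooled contrast. PD − CT and UD − CT taken separately have variance 2/n. A 0.5 SD visit-2 departure then gives 35%, 61% and 89%, and the n = 40 tipping point falls from 0.12 to 0.06. The sizes change; the argument does not.

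Finally, the analysis section is in the past tense, so the model may already have been fitted. That affects how any addition is labelled, not whether it is needed.

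**Conclusion.** The concern holds and should be fixed. Dog versus control, for oxytocin and cortisol alike, is aliased with any departure of visit 2 from the midpoint of visits 1 and 3. With linear visit, which I take to be the more natural reading of the covariate, the bias equals that departure. With categorical visit the contrast rests on the priors. These results follow from the two orders alone and do not depend on sample size. The percentages do depend on assumed n, SD, shift sizes and decision rule, and only convey scale. The documents neither show nor exclude a visit-2 departure. Pet dog versus unfamiliar dog is not affected.

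**What to change.** For the present data, for both hormones:

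1. State how visit was coded. Use one linear term (−1, 0, +1), not a categorical one. This keeps the contrast identified but does not remove the bias.
2. Report the visit slope with its interval.
3. Report dog − CT minus d, where d = (v1+v3)/2 − v2, over at least ± half the estimated visit 1 to 3 difference, then widened to the limits of that half-difference's interval. Give the d at which the conclusion changes.
4. Compare T1 at visit 1 with T1 at visit 3, averaged over both orders, as a check on an arrival response. Compare T1 at visit 2 with the mean of the outer visits. The second check is only partial: T1 precedes the activity, but the child may already know the condition.
5. State that the dog-versus-control conclusion assumes no visit-2 departure beyond the reported range, and that pet dog versus unfamiliar dog does not need this.

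If the analysis is complete, label these additions post hoc.

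The cost is a small analysis of existing data and a more guarded conclusion. In the illustration, with a true effect of 0.50 SD and no visit effect, the conclusion holds over the whole range in 56% of studies (estimated half-difference) or 18% (interval limits) at n = 40, against 73% as planned. At n = 80 it is 88% or 54%, against 95%. Requiring it to hold would cut false conclusions from a first-visit shift to at most 4.5% or 0.4%, but given the loss of power the ranges should be reported as bounds and not used as a pass/fail rule. A peak or trough at visit 2 remains a stated limitation.

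For children still to be scheduled, or a replication, rotate control over all visits, preferably using all six orders. With categorical visit, the pooled variance stays at 1.5 × residual variance / n. A single three-order Latin square contains only 3 of the 6 possible predecessor pairs and does not balance carry-over.

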## Sample Collection, Processing, and Analysis

*Saliva Collection.* Saliva was collected using Saliva Collection Aids from Salimetrics®, or in rare cases where this device presented challenges to children, using a weigh boat.

Before collection began, the experimenter instructed the child on how they should drool into the tube and indicated that the 1 mL mark on the tube is the amount of saliva they are aiming to produce; they were instructed to passively drool into the straw by letting saliva fall into the straw and not to actively spit into it. Children were also told that if they were having trouble producing saliva, they could think of things such as “biting into a lemon” or “thinking of their favorite food.” The experimenter then recorded the initial weight of the micro tube, inserted the collection aid into the tube, and gave it to the child to begin sample collection. When the volume of the saliva had reached or exceeded the 1 mL mark, the straw was removed, and the sample was weighed. If the sample was not at least 1.0 g heavier than the initial weight of the tube, the child was instructed to attempt to produce more saliva. A maximum of ten minutes were allotted for child saliva collection. If the child could not produce enough saliva to reach 1 mL or weigh at least 1.0 g, the weight was recorded and the experiment continued. If a child struggled with the Saliva Collection Aid, a weigh boat was used instead (providing a larger opening in which to deposit saliva); saliva in the weigh boat was then transferred to a microtube using a transfer pipet.

*Saliva processing.* Samples were thawed and centrifuged in a microcentrifuge at 10,000 RPM for 10 minutes. Supernatants from each sample were collected into a new microcentrifuge tube and the pellet was discarded. The supernatant volume was then aliquoted in the following volumes for corresponding analysis: 500  $\mu$ L for oxytocin measurement and 150  $\mu$ L for cortisol measurement. All aliquots were stored again in the -80 °C freezer until analysis.

*Quantitation of salivary oxytocin.* Prior to analysis, salivary samples (500  $\mu$ L) were lyophilized using a CentriVap (Labconco model #7810016) with the following settings: CentriVap: unheated, cold trap: 80–85 °C, vacuum: 0.3–0.4 mbar. When lyophilization was complete, and immediately before assay, samples were reconstituted in 250  $\mu$ L assay buffer (resulting in a two-fold concentration). Samples were assayed in duplicate using a competitive enzyme-linked immunosorbent assay manufactured by Arbor Assays™ (product number K048).

*Quantitation of urinary oxytocin.* Prior to analysis we used a mixed-mode solid-phase extraction following the protocol described and validated by Gnanadesikan et al.. Samples were assayed in duplicate using a competitive enzyme-linked immunosorbent assay manufactured by Arbor Assays™ (product number K048). Urinary oxytocin concentrations were corrected for the specific gravity of the sample using the method described by Gnanadesikan et al..

*Quantitation of salivary cortisol.* Salivary cortisol was measured using a competitive enzyme-linked immunosorbent assay manufactured by Arbor Assays™ (product number K003). Samples were analyzed in duplicate.

## STATISTICAL ANALYSIS PLAN

The **primary outcome measure** was the oxytocin output (relative to baseline) in conditions involving human-animal interaction (pet dog, unfamiliar dog) relative to the nonsocial control condition. The area under the curve with respect to the initial value (AUCi) was used as the measure of oxytocin output. We compared AUCi values across conditions using a Bayesian linear mixed model. In addition to the focal predictor variable (experimental condition), the model included covariates for participant sex, age (years), assay plate, and study visit number. Participant ID was included as a random intercept in the model.

The **secondary outcome measure** was the cortisol output (relative to baseline) in the conditions involving human-animal interaction (pet dog, unfamiliar dog) relative to the nonsocial control conditions. Analysis of this endpoint was conducted identically to that for oxytocin, as described above, with the exception that the model did not include a covariate for assay plate.

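### Does the plan need a written rule for a visit in which one of the three saliva samples cannot be assayed?

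*Combined protocol and SAP*

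**What the plan says.** Under General Procedure, each visit has a baseline sample (T1), a sample 15 minutes into the activity (T2) and a last one: "Timepoint 3 (T3) saliva samples were collected fifty minutes after the start of the behavioral activity".

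Under Sample Collection, Processing, and Analysis, collection is limited to ten minutes. Shortfall is foreseen: "If the child could not produce enough saliva to reach 1 mL or weigh at least 1.0 g, the weight was recorded", and the session carries on. On processing, "The supernatant volume was then aliquoted in the following volumes for corresponding analysis": 500 µL for oxytocin and 150 µL for cortisol. The oxytocin aliquot is dried and taken up in 250 µL of buffer, "resulting in a two-fold concentration". No minimum assayable volume is given, and no order of priority between the two assays.

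Under STATISTICAL ANALYSIS PLAN, "The area under the curve with respect to the initial value (AUCi) was used as the measure of oxytocin output". The model is named in one sentence, "We compared AUCi values across conditions using a Bayesian linear mixed model", and "Participant ID was included as a random intercept in the model". Cortisol is analysed in the same way, without the plate covariate. No section states how a visit with an unusable T1, T2 or T3 is treated.

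**The concern.** AUCi is built from all three concentrations, so one failed assay removes the visit's primary value unless something is put in its place. The protocol expects some children to struggle, yet the SAP does not follow that through. An analyst could drop the visit, join the two remaining points, cut the curve short or carry a value forward, and these give very different numbers. A choice made after seeing the data would leave room for selection.

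Two further points add to the worry. Each child has only one control visit, so losing it removes that child's own dog-versus-control comparison. And the Background says "salivary cortisol was also measured as a biomarker of acute stress, to contextualize findings regarding oxytocin"; if supernatant falls between 500 and 650 µL and one assay goes without, the two hormones could be analysed on different sets of visits.

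**Working it through.** The documents give no sample size, effect size or failure rate, so there is no stated figure to reproduce. The inputs are the sampling times, the aliquot volumes and the model description. T1 is taken as 0 minutes, which is an assumption because baseline is collected before the activity starts.

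**1. AUCi as a weighted sum.** Trapezoid area less the baseline rectangle:

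15(T1+T2)/2 + 35(T2+T3)/2 − 50·T1 = −42.5·T1 + 25·T2 + 17.5·T3.

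With T1 at −10 minutes the weights become −47.5, 30 and 17.5. Either way all three samples are needed.

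**2. What substitute rules would do.**
- T2 missing, T1 and T3 joined by a line: 50(T1+T3)/2 − 50·T1 = 25(T3−T1).
- T3 missing, curve cut at 15 minutes: 15(T1+T2)/2 − 15·T1 = 7.5(T2−T1).
- T3 missing, T2 carried forward: 42.5(T2−T1), which is 42.5/7.5 = 5.67 times the cut value.

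For an assumed profile of 100, 150, 100 the full AUCi is 25×50 = 1250. The three rules give 0, 375 and 2125. The spread is wide, but it exists only if such a rule is used, and the documents mention none of them.

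**3. How short a sample can be.** Both assays need 500 + 150 = 650 µL, which is 65% of the 1 mL target; oxytocin alone needs 50%. A sample below target is therefore not necessarily a failed one. The loss to the discarded pellet is not given.

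**4. How many visits could be lost.** Let each sample fail independently with assumed probability p. Then v = (1−p)³ is the chance that a visit is complete. A child keeps a within-child dog-versus-control comparison if the control visit and at least one dog visit are complete: v[1−(1−v)²].

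| p | Visits without AUCi, 1−v | Children with at least one such visit, 1−v³ | Children with no within-child dog-versus-control comparison |
|---|---|---|---|
| 1% | 3.0% | 8.6% | 3.1% |
| 2% | 5.9% | 16.6% | 6.2% |
| 5% | 14.3% | 37.0% | 16.0% |
| 10% | 27.1% | 61.3% | 32.5% |

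Independence is pessimistic if difficulty runs in particular children, as the protocol's wording about a child who struggles suggests. With an assumed intra-child correlation of 0.3 at p = 5%, 10.8% of visits are lost rather than 14.3%, and 81% of children are complete rather than 63%.

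**5. What dropping visits costs in precision.** The comparator is a model on the individual concentrations, which can use partly observed visits. The calculation assumed 40 children, known covariances, within-visit correlation of 0.3 or 0.6 and no plate terms; the known covariances and missing plate terms tend to favour the comparator. The variance of the pooled dog-versus-control contrast was 1.017–1.023 times as large at p = 1% and 1.033–1.047 times at 2%. Taking square roots, the standard error is about 1% to 2% larger. At 5% and 10% the variance ratios were 1.087–1.127 and 1.195–1.273, so the standard error is about 4% to 6% and 9% to 13% larger.

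**6. Short oxytocin aliquots.** An assumed 400 µL aliquot taken up in 250 µL is concentrated 400/250 = 1.6-fold. Read as two-fold it comes out at 1.6/2 = 80% of its true value. On a flat profile of 100, such an error at T1 alone gives −42.5×80 + 25×100 + 17.5×100 = 850. This would matter, but it supposes both that a short aliquot was assayed and that nobody corrected for its volume. The processing section specifies 500 µL, and nothing suggests otherwise.

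**The case for a change.** The strongest case for acting is that a default nobody wrote down is not a rule. Writing it takes a few sentences, and the primary endpoint depends on it. The default is also not assumption-free. Dropping visits is unbiased only if, given condition, covariates and the child's other visits, the loss is unrelated to the AUCi that would have been seen. If a condition affects both hormone levels and the ability to produce saliva, that could fail, and the plan does not ask for losses by condition.

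The omission itself stands, and so does the caveat about missing at random. What does not follow is that the plan yields a wrong result. No documented step produces one, and a written rule to drop incomplete visits would rest on the same assumption. A model on the individual concentrations would use the partial visits, but it brings many more parameters (covariates and child effects by time) and its own distributional assumptions. As a sensitivity analysis it would leave the primary result as it is, and a reasonable statistician could decline it.

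Nor is there a general bias figure to set against the plan. If two-point values were used at 10% failure, the contrast would shrink by 11% to 16% when T2 rises by 1 and T3 by 0 to 1. It would shrink by 5% when only T3 rises, and grow by 20% for a T2 fall of 0.5 with a T3 rise of 1. The documents give no response profile, so neither direction nor size is fixed. Finally, the text is written in the past tense; a rule added now would disclose what was done, not guard against choosing it after the data were seen.

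**Conclusion.** This is missing detail that analysts fill sensibly, not a flaw in the method. A visit without three valid samples has no AUCi and drops out of the model, while the random intercept keeps the child's remaining visits. Oxytocin and cortisol are modelled separately, so slightly different sets of visits invalidate neither analysis.

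The size is unknown because no failure rate is given. At an assumed 1% to 2% per sample, 3.0% to 5.9% of visits are lost and the standard error rises by about 1% to 2%, under the assumptions stated above. At 5% to 10% the loss would be material, but nothing in the documents points to a rate that high. The conclusion rests on losses being missing at random, on incomplete visits being dropped rather than patched, and on oxytocin aliquots being the specified 500 µL or corrected for actual volume. A results report would normally confirm these points and count lost samples and visits by condition and timepoint. The plan itself needs no change.

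### Should the cortisol model adjust for assay plate, as the oxytocin model does, and for time of day?

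*Combined protocol and SAP*

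**What the plan says.** The section STATISTICAL ANALYSIS PLAN states that for oxytocin "the model included covariates for participant sex, age (years), assay plate, and study visit number", alongside condition, and that "Participant ID was included as a random intercept in the model". The outcome is a change-from-baseline area: "The area under the curve with respect to the initial value (AUCi) was used as the measure of oxytocin output". The cortisol analysis is declared identical, "with the exception that the model did not include a covariate for assay plate". No reason is given, and clock time appears in neither model.

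Under Sample Collection, Processing, and Analysis, "Salivary cortisol was measured using a competitive enzyme-linked immunosorbent assay", in duplicate, as for oxytocin. The number of cortisol plates, their layout and the inter-plate variation are not stated. The Background gives cortisol's role: "salivary cortisol was also measured as a biomarker of acute stress, to contextualize findings regarding oxytocin".

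**The concern.** Two closely similar immunoassays on the same saliva samples are treated differently. Plate counts as a nuisance worth a covariate for one hormone and is dropped for the other without comment, which can look discretionary. Cortisol is also commonly expected to drift with time of day (taken here as an assumption, since the documents do not discuss it), and no term absorbs that.

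The stake is interpretive. Oxytocin may rise with pleasure or with stress, and cortisol is there to help tell them apart. Extra noise makes a finding of no cortisol difference easier to reach. If plate or appointment hour happened to go with condition, the dog-versus-control contrast would be biased.

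**Working it through.** **Inputs.** The sample times are in General Procedure: the experimenters "returned 15 minutes later to collect timepoint 2 (T2) saliva samples from the child", and "Timepoint 3 (T3) saliva samples were collected fifty minutes after the start of the behavioral activity". T1 is set at 0 minutes (nominal). The documents give no sample size, SD, plate count, plate variation or visit hours. There is therefore no plan figure to reproduce, and every range below is a labelled assumption.

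**1. AUCi weights.** The trapezoidal area is 15(T1+T2)/2 + 35(T2+T3)/2 = 7.5 T1 + 25 T2 + 17.5 T3. Subtracting 50 T1 gives AUCi = -42.5 T1 + 25 T2 + 17.5 T3. The weights sum to 0, so a constant added to all three samples of a visit drops out. Multiplicative calibration differences, or one visit split over plates, do not drop out.

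**2. How many plates?** 3 visits x 3 samples x 2 wells = 18 wells per child. On a 96-well plate (assumed), 96/18 = 5.3, so at most 5 children fit, before standards. Several plates are likely. The same count shows that one child's samples fit easily on a single plate, in which case plate is constant within child and, with complete data, a plate term leaves the condition contrast unchanged.

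**3. Size of the plate effect when a child's visits sit on different plates.** A calibration error d shifts AUCi by d x AUCi. Relative to the within-child SD, the plate SD is CV x (mean AUCi/SD).
- Low end: 0.10 x 0.5 = 0.05; variance share 0.05² = 0.25%; SE inflation √1.0025 = 1.001.
- High end: 0.15 x 1.5 = 0.225; variance share 0.225² = 5.1%; SE inflation √1.051 = 1.025.

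So at most about 2.5% of the SE is recoverable.

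**4. Does adjustment cost anything?** The crossover was simulated with 20-50 children, 3-10 plates and plate SD 0-0.6 of the within-child SD (all assumed), with plate as a fixed effect. The SD of the dog-versus-control estimate with plate, divided by that without, was:
- 1.00 when each child stays on one plate;
- 0.90-1.16 when visits fall on plates at random;
- 0.55-1.73 when plates are partly aligned with condition.

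The 10% gain needs a plate SD of 0.6, well above the 0.225 in step 3. A random plate intercept is milder (20 or 45 children, 4 or 9 plates): 0.87-1.01 with random placement and 0.71-1.16 with partial alignment.

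**5. Time of day.** A constant slope s per minute adds s(25 x 15 + 17.5 x 50) = 1250 s to every AUCi and cancels between conditions. Only a slope that changes over the day remains. With exponential decline at rate k per hour (assumed), AUCi/T1 = -42.5 + 25e^(-0.25k) + 17.5e^(-0.833k). Two visits g hours apart then differ by |AUCi|(1 - e^(-kg)), in units of the T1 level at the visit with the earlier clock time:

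| k per hour | AUCi level | 1 h apart | 3 h apart | 6 h apart |
|---|---|---|---|---|
| 0.10 | -2.02 | 0.19 | 0.52 | 0.91 |
| 0.15 | -2.98 | 0.41 | 1.08 | 1.77 |
| 0.25 | -4.81 | 1.06 | 2.54 | 3.73 |

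A sustained 10% response at T2 and T3 (an assumed benchmark; the plan names no target effect) gives 0.10 x 42.5 = 4.25. The differences are 0.19/4.25 = about 5% to 3.73/4.25 = 88% of that. The levels of -2.0 to -4.8 are close to the benchmark, but they are present at every visit and are not what separates conditions.

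If clock time explained 2-30% of within-child variance (assumed), adjusting for it would cut the SE by 1 - √0.98 = 1% to 1 - √0.70 = 16%.

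**The case for a change.** The best case for a change is this. Several plates are almost certain, AUCi does not remove calibration differences, and nothing says that a child's samples were kept together. A random plate intercept shrinks when plates agree, so it costs little: in the simulations its worst loss, 16%, came only with 4 aligned plates, 20 children and no plate effect, and every other setting was at 1.04 or below. Control is always the second visit, so plates loaded in visit order would align with the very contrast of interest. Appointment hours could do the same.

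Much of that stands as description. The omission is real and unexplained, and the proposed plate term is mostly harmless. But a harmless term is not a needed one, and its benefit at plausible plate variation is a few percent of the SE at best. The alignment argument is conditional on a loading order and a schedule that the documents do not describe. If alignment were complete, plate and condition could not be separated by any covariate. Clock-time adjustment needs recorded times, which the documents do not mention, and its absence is common to both models, so it is not an inconsistency. The plan is also written in the past tense, so replacing the cortisol model now would be a post hoc choice.

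**Conclusion.** No change to the plan. The difference between the two models is a missing explanation on a secondary, contextual outcome, and analysts can cover it by reporting the plate layout. Under a calibration CV of 10-15% and a mean AUCi of 0.5-1.5 SD, omitting plate costs about 0.1-2.5% of the standard error; with each child on one plate, adjustment gains nothing. For time of day, the common part of any decline cancels within child. The remainder comes near a 10% response only at the fastest assumed decline with visits six hours apart. It acts as noise unless visit hour differs by condition.

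The conclusion rests on plate and hour being unrelated to condition. The documents neither support nor contradict that. Evidence of such alignment would reopen the question. A labelled sensitivity analysis would be reasonable if the run sheets and times exist, but it is a preference and does not correct an error.
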